4.1 OVERVIEW OF STUDY DESIGN/INTERVENTION

4.2 Design

This study is proposed to be carried out across a two year period including an intervention period and dissemination of results to the Taxi Network community. Twenty eight non-smoking male NYC cab drivers will be recruited and randomized to one of two study arms, an Intervention Group (to receive the HEPA filter 2 weeks into their 4 week period of participation) and a Wait-list Control Group (to receive the HEPA filter at the end of their 4 weeks of participation). For the Intervention and Wait-list Control Group drivers, during the first 2 weeks, measurements (e.g. biological markers and air monitoring) will be taken under usual conditions. At the end of the initial two weeks, portable HEPA air purifiers (136) will be placed in the Intervention Group drivers' cars and the air monitoring and biological parameters will be repeated for another 2-week period, to determine changes in PM levels and physiological measurements as a result of this targeted intervention. The Wait-list Control Group drivers will not receive a HEPA air purifier at this time, but will also have the air monitoring and biological parameters repeated for another 2 weeks. At the end of the 1 month period of measurements for both groups of drivers, the Wait-list drivers will then receive a HEPA air purifier, so that they may also potentially benefit from the intervention being tested in this study, but no further measurements will be taken. Drivers will serve as their own controls before/after work and before and after the intervention.

Our taxi network CAB (Community Advisory/Action Board) will be engaged in the implementation and dissemination of the proposed study. This Taxi CAB represents the full range of the taxi driver experience, including varied shifts, income, education, age, ownership/lease arrangements, and countries of origin. The Taxi CAB will be instrumental in study recruitment and dissemination of results. The CAB will meet quarterly, with additional meetings as needed. This study is conducted in collaboration with Drs. [name] and [name]'s research teams at New York University Department of Environmental Medicine, and [name], working from the City College of New York (CCNY). Biological specimens collected will be immediately transported to MSK BAIC Core facilities for temporary storage and will be shipped later to either NYU or CCNY (outlined in the assessment and evaluation-section 7).

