4.3 Intervention

Over the course of the study, we will monitor several biological and physiological markers associated with lung cancer and CVD risk, along with ongoing air monitoring of work-sites and residences of all study participants. HEPA filters were selected as the intervention because of their effectiveness in removing PM and volatile organic compounds (VOCs), ease of use, relatively low-cost, small size, light weight, and lack of interference with drivers' normal practices (136). In a previous study by Pui et al., placing the air recirculation mode on (and with a cabin air filter in place already installed by the car manufacturer, not all cars have cabin air filters), was successful at substantially removing ultrafine particles, although was still relatively inefficient (45.5% particle removal efficiency) compared to a HEPA filter (137).

The study will require 4 weeks of participation. Drivers will be recruited and randomized to either the control condition or the HEPA filter intervention condition. The in-vehicle (for all drivers PM exposure levels and physiologic and biochemical markers will be measured over the course of 1 month. For the first two weeks of the 1-month period, measurements will be taken under usual conditions (*without HEPA filters*) for all participants.

Particulate matter concentrations will be measured/monitored through *Personal DataRams* (pDR) (*personalDataRam*[™] model pDR-1200). The DataRam measures particulate matter through optical impedance, and produces per-minute averages. Therefore, the time that the DataRam is —onll will be directly reflected in the data that is produced. The pDR is 24 ounces, 6.3 inches in height, 8.1 inches in width, and 2.4 inches in depth, and is thus very portable. One pDR will be provided to each enrolled participant. All participants will monitor PM at their homes in the room in which they spend most of their off work hours; the DataRam will then be moved to the bedroom at night (or during sleeping hours). For drivers, the pDR will record PM levels throughout the work shift while the vehicle is in motion, momentarily stopped, or parked.

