Following informed consent, participants will be assigned a participant number and administered the Intake Assessment (Appendix B). Participant drivers will also be randomized to either the Intervention or Wait-list Control Groups, as described above. A convenient time and place will then be arranged to complete the informed consent and Intake. Driver pairs will participate in the study in approximately the same time frame to avoid seasonal differences in PM levels.

During consent procedures, participants will be informed that they will receive a \$200 incentive over the course of the study for their participation to account for the time commitment required of participants. This will be distributed as 4 weekly incentives totaling \$50.00 each, which can be viewed as compensating study participants \$7 each day for carrying around monitors throughout their daily lives and allowing us to conduct biologic assessments 2 days a week. All participants will also be informed that they will receive a HEPA air purifier. Given the intensity of the proposed study measurements and the

associated time required of participants, for which drivers could result in lost earnings, the \$200 incentive is commensurate with the degree of commitment demanded.

Consenting professionals will emphasize the need to meet with participants 2 days a week to conduct study testing, and will discuss and compile a list of 2-3 future meeting locations for data collection. Convenient locations may include enclosed taxi garages, taxi relief stands, semi-private spaces within public venues, MSKCC offices or our community partner locations. Staff will not conduct any assessments at a participant's home.

During the initial conversation between the investigator/research staff and the potential study participant, the potential participant may be asked to provide certain health information that is necessary to the recruitment and enrollment process. They will use the information provided by to confirm that the potential participant is eligible and to contact the participant regarding study enrollment. If the person turns out to be ineligible for the research study, the research staff will destroy all information collected on the patient during the initial conversation, except for any information that must be maintained for screening log purposes.

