7.1 ASSESSMENT/EVALUATION PLAN

All potentially eligible participants will be required to complete a study screening tool to confirm eligibility. Participants that undergo informed consent procedures will be required to complete an intake assessment to gather details on personal demographics and health information that may relate to study outcomes. Enrolled drivers will be provided a log to compile a detail account of vehicle air-flow conditions while driving during study participation.

Screening tool (Appendix A), a brief questionnaire administered to potential to assess if study eligibility requirements are met. Includes questions on age, residence, country of origin, previous travel and travel intentions, modified BRFSS tobacco use classification questions (160); English proficiency, smoking status, cab driving experience, current occupation(s), and status of pre-existing conditions relevant to study (e.g. sleep disorders, autoimmune conditions). (5 min to complete)

Intake assessment (Appendix B) administered to all study participants includes 3 sections of questions: (1) demographic and health access information, (2) medical history and (3) physical activity and nutrition. (10-15 min to complete)

Log-book (Appendix C), given to drivers to record environmental manipulations within the area they are driving or their vehicle. This includes air exchange levels within the cab (documenting whether the DataRam is used, HEPA filter and air conditioning is on, vents and windows are open, the vehicle make or model of taxi cab or the neighborhoods driven in during shift). This also includes documenting neighborhoods travelled thru, whether they were in high traffic jams, or travelled thru tunnels. In our preliminary work (X12-021), we have succeeded in encouraging drivers to complete a similar log-book. When we meet with drivers to conduct biological measurements, or contact them for any other reason, we will remind them to complete their log-books using the text reminder system described below.

During biological assessments (2 days per week), the make and model of the vehicle used by driver participants will be logged by study staff to account for variances within the current air filtration systems of the cab, because taxi drivers may rent different vehicles each day.

Environmental Measurements, Physiologic and biochemical markers

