In-vehicle and residence PM will be measured using calibrated, personal DataRam monitors (Thermo Scientific) that measure real-time PM levels (measured range = 1 μg to 400 $\mu\text{g}/\text{m}^3$). For drivers, the DataRam will be placed inside the cab on the island between driver and front passenger seat during workshifts. All participants will monitor PM at their homes in the room in which they spend most of their off work hours; the DataRam will then be moved to the bedroom at night (all participants will receive daily text messages as reminders to do this). The DataRam will be zeroed prior to use and all data internally logged and displayed on an LCD monitor. DataRam PM measurement files (hourly averages) will be downloaded every week at the same time as blood/ salivary samples are taken. To maximize efficiency in the field, gravimetric calibration will be performed by comparison with a filter sampler and programming of a calibration constant. Teflon and quartz filters will be used to capture PM (a time-averaged sample) for subsequent gravimetric and trace element analyses, including sulfur and organic and elemental carbon analyses (micro-balance/XRF instrumentation available at NYU's NIEHS Center of Excellence Facility Core). A portion of the glass-fiber filter will be cut for organic analysis. This portion of the filter will be extracted via pressurized liquid extraction (ASE 100 system, Dionex) with hexane: dichloromethane (1:1, v/v) at 90°C and 1500 psi (140). The extracts will be concentrated using a Turbopap and cleaned before analysis. BFRs polybrominated diphenyl ethers (PBDEs) will be analyzed via gas chromatography-mass spectrometry with negative chemical ionization (GC-NCI-MS) (141). Parent PAHs will be analyzed with GC-MS in electron impact ion (EI) mode and selected ion monitoring (SIM), whereas nitro-PAHs and oxy-PAHs (quinones) will be analyzed via GC-NCI-MS and SIM (142). Another portion of the glass-fiber filter will be cut for metal analysis. This portion of the filter will be extracted via microwave digestion and trace metals will be analyzed via inductively coupled plasma-mass spectrometry (ICP-MS) according to the method of Kulkarni et al.(143).

DataRam data downloads will be sent to study collaborators Drs. [name] and [name] at NYU for analysis.

2. Black carbon exposure (measured at minimum after 1 work shifts during week 1 and week 4, at maximum will be measured after 3 work shifts every week)

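### The PM monitor beside the driver has a live display that the supplied text does not mask, so drivers could react to readings of the outcome; covering it is a cheap improvement

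*Combined protocol and SAP*

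**What the plan says.** **The monitor and its display.** Section 7.1, item 1, describes a real-time instrument: "The DataRam will be zeroed prior to use and all data internally logged and displayed on an LCD monitor". During work, "the DataRam will be placed inside the cab on the island between driver and front passenger seat during workshifts". At home it stays in the room the driver uses most, and "the DataRam will then be moved to the bedroom at night". Section 4.3 gives each participant one unit and says "the pDR will record PM levels throughout the work shift while the vehicle is in motion, momentarily stopped, or parked". The time-point table in section 7.1 schedules PM every day of a 28-day study period.

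**The two periods.** Section 4.2 says that, for both arms, "during the first 2 weeks, measurements (e.g. biological markers and air monitoring) will be taken under usual conditions". Section 4.3 uses the same expression and glosses it as meaning that no HEPA filter is present. After week 2 the intervention arm gets a purifier; "The Wait-list Control Group drivers will not receive a HEPA air purifier at this time". No sham device or masking is described.

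**What drivers record.** The log-book in section 7.1 covers changes to the cab environment, including "documenting whether the DataRam is used, HEPA filter and air conditioning is on, vents and windows are open", together with neighbourhoods, traffic jams and tunnels.

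**What is analysed.** Section 9.1 lists PM exposure first among the primary outcomes. Section 11.0 takes the Aim 2 result as the difference between the two conditions in the PM components and the markers. It does not mention the log-book.

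**The concern.** A participant who can see a running measure of the outcome, and who can also influence that outcome, may change his behaviour. The driver controls the windows, vents and air conditioning, has some choice of route and, in one arm, operates the purifier.

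Two estimates are exposed. Aim 1a is meant to describe PM exposure in taxi work, and if drivers respond to the reading in weeks 1-2, that description moves away from what unmonitored drivers experience. Aim 2 compares the arms. After week 2 a filter driver could use the reading to adjust the purifier and the cabin around it, whereas a wait-list driver could respond only by other means. Part of the observed difference would then be a response to the display rather than the effect of the filter.

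Drivers cannot readily be blinded to a purifier in their own cab, but no stated procedure requires them to see the PM value. This route to bias is avoidable, and it cannot be removed after the data are collected.

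**Working it through.** The plan gives no figure for reaction to the display, so there is nothing to reproduce. The check sets the relevant sections side by side.

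1. **Is a reading available to the driver?** Section 7.1, item 1, establishes a real-time instrument, an LCD and a position beside the driver. It does not state which way the screen faces, whether it stays lit, or whether drivers look at it. The documents support availability, not actual viewing.

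2. **Is the reading masked anywhere?** Sections 4.2, 4.3, 7.1 and 11.0 contain no instruction to cover or switch off the display, or to keep ventilation habits unchanged. Section 7.1 refers to the RSA guide/lab manual for full procedures, and that manual was not supplied.

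3. **Does the driver need the reading?** Data are logged internally and downloaded weekly (section 7.1, item 1). Adherence is prompted by text messages and a door-knob sign (section 7.1). No stated procedure depends on the driver reading a concentration.

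4. **Could behaviour change in-cab PM?** Section 4.3 cites a study in which recirculation with a cabin filter removed 45.5% of particles, reported there for ultrafine particles, and brought cabin aerosol below typical office levels in about 3 minutes. Ventilation settings can therefore matter, and quickly. The figure does not say how many drivers would change settings, and it is not a result for DataRam mass, so it gives no estimate of bias here.

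5. **Would the effect differ by arm?** Both arms carry the same monitor, so the display alone is symmetric. A differential effect needs the display to interact with something that differs, namely the visible purifier after week 2. Knowledge of allocation could also play a part: section 6.0 says "Participant drivers will also be randomized to either the Intervention or Wait-list Control Groups, as described above", which places randomization before the two-week baseline, but the plan does not say whether drivers are told their arm then.

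6. **Which direction?** Avoidance by wait-list drivers would shrink the difference; better purifier use or cabin closure by filter drivers would enlarge it. The documents do not allow the two to be weighed.

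7. **Is the behaviour captured?** Largely. The log-book covers HEPA use, air conditioning, vents, windows, neighbourhoods and tunnels. Section 7.1 does not name recirculation, and describes the log as covering the vehicle and the area driven, not the home. Section 11.0 assigns these data no role in the Aim 2 comparison.

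**The case against.** The strongest case against has four parts.

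- **Viewing is inferred.** A reader might conclude that the reading is in the driver's view throughout. The documents give the placement and the LCD, not the screen's orientation or use, and the lab manual may already deal with it. This stands, and it limits the point to a possibility the supplied text leaves open.
- **Usual conditions has a narrower meaning.** A reader might infer that weeks 1-2 fail the protocol's own definition. Section 4.3 defines the term by the absence of HEPA filters, and a visible display does not breach that. What remains is the separate question of whether the period represents unmonitored driving.
- **The log-book already records most of the behaviours.** This stands as mitigation. However, recording is not analysis, and adjusting afterwards for self-reported behaviour that follows randomization is weaker than removing the prompt.
- **Motivation and consequence may be small.** In the preliminary survey (section 3.0), 34% of drivers were not worried about exposure while driving and 40% were a little or somewhat worried, although 81% thought air pollution causes health problems. Peaks were short and sporadic, and the analysis averages hourly values over the day, which dilutes reactions to brief spikes. Section 11.0 limits the study to descriptive statistics, so no test is at risk. This lowers the severity but does not show that the risk is absent.

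A cover would also leave open allocation, daily text reminders and self-recording of ventilation in place, so it removes one source of reactivity and not all of them.

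**Conclusion.** The point holds as a low-severity, cheaply avoided weakness in a descriptive pilot. The supplied text places a live PM display beside unmasked drivers for 28 days, gives the reading no stated purpose for them, and neither masks it nor plans to use the log-book that would show any response. This could make the weeks 1-2 description of exposure less representative, and could bias the Aim 2 PM difference after week 2.

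The size and direction of either effect are unknown. Any figure would rest entirely on an assumed rate of reaction, so none is offered. A reader might infer that the Aim 2 difference is demonstrably biased in one direction. The documents do not support that, because the display is the same in both arms and the plausible responses pull in opposite directions.

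The conclusion assumes that the screen can be read from the driver's seat or at home and that the lab manual does not already cover it. If the manual does, the remaining issues are a confirming sentence in the protocol and use of the log-book. The consequence is a possible distortion of pilot estimates intended to guide a larger trial, not a false-positive finding.

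**What to change.** **Section 7.1, item 1.** State that the concentration display is covered for all participants in both arms from day 1 to the end of participation; that staff confirm at the weekly download that the unit has been logging; and that a driver's PM results are not given to him until his participation ends. Repeat this in the lab manual or, if the manual already says it, cross-refer to it.

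**Section 11.0, Aim 2.** Add a descriptive table of log-book ventilation (windows, vents, air conditioning) and HEPA use by arm and by period (weeks 1-2 and weeks 3-4), presented beside the PM difference. This shows whether behaviour diverged without needing a model.

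**Cost.** One opaque cover per monitor, a short protocol addition and one table from data already being collected. The downside is that drivers cannot use the reading to check that the unit is running. The cover should leave any on/off indication visible, and should be tried in the equipment trial runs that section 4.3 already plans before enrolment.

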3.0 BACKGROUND AND RATIONALE

There are approximately 240,000 taxi/limousine drivers in the U.S. (1). By 2020, this number is expected to increase by 20% (1). New York City (NYC) is home to 100,000 taxi drivers, among whom 92% are immigrants (2, 155). Forty percent of those are South Asian (originating from India, Pakistan, Bangladesh, Nepal, and Sri Lanka) (2), followed by large numbers of drivers from the Dominican Republic, Mexico, former USSR, Haiti, Nigeria, Ethiopia, Columbia, Ecuador, and Jamaica (2). The overwhelming majority of taxi drivers are minority men. They are at great risk for increased cancer risk and poor cardiovascular health due to a number of occupation-related factors, including stress, diet, sedentary lifestyle, and poor health care access (18-21).

They work long hours (10-12 h/d shifts, ~6d/wk (2)), most often in heavy traffic, and are exposed to environmental contaminants. This exposure, including to ambient particulate matter (PM) (even low-level exposure to fine airborne PM [PM smaller than 2.5 micrometers (PM_{2.5})]), increases health risk (13, 22, 23). Even short-term exposure (i.e., while driving) to peak particle concentrations appears to be linked with adverse health effects (24-27). A vehicle cabin is a relatively confined space where drivers are exposed to high concentrations of PM. In comparison to outdoor/indoor microenvironments, in-vehicle PM levels are often very high, originate from external sources, including road traffic (28), and can be 3-5 times that of outdoor PM values (29). In a study examining PM levels in private cars, values in moving vehicles exceeded those in parked cars by 9.2 times for PM₁₀ (PM smaller than 10 micrometers) and 3.8 times for PM_{2.5} (28). These conditions can potentially be improved at very low cost, with a HEPA filter, with a resultant diminution of lung cancer and cardiovascular disease (CVD) risk in this vulnerable group of minority men.

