
experience. Thirty-four percent of respondents stated they were —not worriedll about being exposed to air pollution while driving, while another 40% said they were —a little or somewhat worriedll. Nineteen percent reported that they believed they had a health problem attributable to air pollution exposure. In [name] protocol X12-021, a pilot investigation of particulate matter concentrations in NYC taxi cabs, we measured levels of in-vehicle Particulate Matter (PM) concentration in a convenience sample of 7 NYC Taxi Cabs. In-vehicle PM levels were measured through *Personal DataRams*(pDR) and *Microaethalometers*, which were placed on the passenger seat or console area of the taxicab for the full 6-hour shift. Near-roadway outdoor air monitoring of PM and BC concentrations was also conducted using aerosol monitors. Compared with previously published results of personal exposure studies conducted in NYC (156, 157), taxicab PM and BC concentrations were elevated. Average concentrations of PM per 15-minute interval for all seven shifts indicated large intra- and inter-car variability. Per shift average PM concentrations ranged from 4 $\mu\text{g}/\text{m}^3$ to 49 $\mu\text{g}/\text{m}^3$ and 1-minute peak levels measured up to 452 $\mu\text{g}/\text{m}^3$. Black carbon levels were also elevated, and reached over 10 $\mu\text{g}/\text{m}^3$. Peak in-vehicle PM levels were short and sporadic, and may have been influenced by external events, such as passenger smoking, as recalled by drivers after their shift. Roadside air monitoring was conducted at three large taxi passenger pick-up stands in midtown Manhattan, all located at traffic hubs and mass transport terminals. Monitoring during morning and evening rush hours revealed ambient PM levels to be near or greater than the EPA 24 hour NAAQS of 35 $\mu\text{g}/\text{m}^3$ for $\text{PM}_{2.5}$. Average levels at each taxi stand were 44 $\mu\text{g}/\text{m}^3$ (SD \pm 32), 58 $\mu\text{g}/\text{m}^3$ (SD \pm 10), and 76 $\mu\text{g}/\text{m}^3$, (SD \pm 43) and peak levels were as high as 434 $\mu\text{g}/\text{m}^3$, mirroring peak in-vehicle values. Levels of black carbon were also found to be high; peak levels at one taxi stand were as high as 12 $\mu\text{g}/\text{m}^3$. Average taxi stand BC and PM levels were significantly higher than levels recorded at the closest New York State Department of Environmental Conservation's air monitoring site (Division Street) (158). As a sedentary occupational group with a disproportionate prevalence of disease, taxi drivers are likely at greater risk from air pollutant exposure than those working away from roadways. Community-engaged interventions are needed to limit their exposure to high levels of PM and BC. The proposed DRIIVE project will move the preliminary data a step forward and the CAB will continue to play a central role in planning, implementation, and dissemination.

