9.1 PRIMARY OUTCOMES

The primary outcomes are:

- To collect preliminary data on in-vehicle excess PM exposure the personal DataRam will monitor/report the PM levels as time-averaged sample (hourly averages) that will be monitored at work site and at homes across all groups
- To conduct a preliminary assessment of the correlation between PM exposure and physiologic and biochemical markers associated with increased risk of lung cancer and CVD the personal DataRam will monitor/report PM levels (hourly averages) that will be analyzed in comparison to increased systolic blood pressure, reduced heart rate variability, and presence of biological markers related to lung cancer and CVD risk.

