11.0 BIOSTATISTICS

Overview. This pilot study follows a two parallel arm design. Drivers will be randomized to one of two groups, an Intervention Group (an in-vehicle HEPA filter will be provided) and a Wait-list Control Group (HEPA filter will be provided at the end of wait-list period). We plan to recruit a sample of n=14 participants in each group (n=11 per arm with analyzable (non-missing) data, assuming a 25% drop-out rate as described below).

General analytic strategies. The general data analytic paradigm for this pilot study will be descriptive statistics only. The aim is to collect pilot data to help guide a future randomized intervention study. Descriptive statistics and assessments of correlations will be sought to address the aims (see below). The sample size of 14 per condition was primarily determined by resources limitations. A sample of 14 per condition was deemed possible within the funding resources of no more than 2 years.

Analytic plans for the Specific Aims.

Aim 1a: The primary aim will be to collect preliminary data on in-vehicle excess PM exposure.

Descriptive statistics (means and standard deviations) will be sought on: 1) PM size distribution 2) mass concentration, and 3) chemical composition for all three groups. These observations will be used to evaluate to what extent the two groups were exposed to these environmental hazards. For each study participant, an area-under-the-curve (AUC) summary will be sought for each of the three PM measurements over appropriate time periods. Generally, a daily average will be calculated from the hourly PM assessments. Then the AUC of the 28 daily averages will be calculated per person to represent the summary of PM exposures during study participation.

Aim 1b: To conduct a preliminary assessment of the correlation between PM exposure and physiologic and biochemical markers associated with increased risk of lung cancer and/or CVD.

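### In-vehicle PM is planned from hourly files and whole-day averages; one-minute records and a cab-only shift mean would measure it more cleanly at little cost

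*Combined protocol and SAP*

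**What the plan says.** Section 4.3 (Intervention) describes the monitor's output: "The DataRam measures particulate matter through optical impedance, and produces per-minute averages". Each participant gets one unit, used in the cab during shifts and at home otherwise.

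Section 7.1, item 1, says the unit is zeroed before use, with "all data internally logged and displayed on an LCD monitor". On what is collected it says "DataRam PM measurement files (hourly averages) will be downloaded every week". The stated measuring range ends at 400 µg/m³.

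Section 9.1 (Primary Outcomes) refers to hourly averages in both of its entries. Section 11.0, Aim 1a, continues: "Generally, a daily average will be calculated from the hourly PM assessments". An AUC of the 28 daily values then gives one PM summary per person. Aim 1b leaves the time-linkage of PM and biomarkers to be settled after the data are in. Aim 2 compares the arms on PM without defining a further summary.

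Section 2.0 words Aims 1a and 2 in terms of in-vehicle PM, with Aim 1a measured at work and at home. Section 3.0 mentions peaks twice: "Even short-term exposure (i.e., while driving) to peak particle concentrations appears to be linked with adverse health effects", and, in the preliminary studies, "Peak in-vehicle PM levels were short and sporadic". That pilot reports shift averages of 4 to 49 µg/m³ and one-minute values up to 452 µg/m³.

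**The concern.** The exposure that Aims 1a and 2 address is the air in the cab. The instrument can resolve the minute at which the driver starts or ends a shift, but every later step named in the plan is coarser. An hour in which the monitor changes place gets one value for two environments, and no rule is given for splitting it. The daily average then pools cab and home time altogether.

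Two things are at stake. First, a filter that works only in the cab will look weaker on a whole-day PM summary than it is in the vehicle, and these pilot figures are meant to guide a larger trial. Second, brief peaks cannot be recovered from hourly values. Blood pressure is taken immediately before and after a shift, so its natural exposure window is the shift, which need not align with clock hours. An analysis can be revised later; a record that was never downloaded may not be recoverable.

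**Working it through.** The plan gives no figure of its own on this point to reproduce. The inputs are:

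- shift length 10-12 h, about 6 days a week (Sections 1.0 and 3.0);
- one-minute output (Section 4.3), hourly files (Section 7.1), then daily average and 28-day AUC (Section 11.0);
- pilot one-minute maximum 452 µg/m³ and shift means 4 to 49 µg/m³ (Section 3.0).

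Assumptions: bins are clock hours, shifts last a whole number of hours and start off the hour, the monitor runs all day, and the lowest and highest pilot shift means serve as backgrounds.

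**Shift boundaries.** A shift of L hours starting off the hour touches L + 1 bins, of which 2 are mixed.
- L = 10: 2/11 = 18% of bins are mixed. Non-cab time is 1 h of 11 h = 9%.
- L = 12: 2/13 = 15% of bins are mixed. Non-cab time is 1 h of 13 h = 8%.
- Using only the full bins leaves pure cab air but covers 9/10 = 90% or 11/12 = 92% of the shift.

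**Daily average.** Cab share of a work day is L/24.
- 10/24 = 42%; 12/24 = 50%.
- Over a week with 6 work days: 10/24 × 6/7 = 36%; 12/24 × 6/7 = 43%.

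If home air is unchanged, a given change in cab PM therefore appears in the whole-day mean at 42-50% of its size on a work day, and at 36-43% of its size averaged over the week. This mixing is several times that at the shift boundaries.

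**Peaks.** The hourly mean of a peak P lasting m minutes on background b is (P·m + b·(60 − m))/60.
- m = 1, b = 4: (452 + 59 × 4)/60 = 11.5.
- m = 1, b = 49: (452 + 59 × 49)/60 = 55.7.
- m = 5 (assumed), b = 4: (5 × 452 + 55 × 4)/60 = 41.3.
- m = 5 (assumed), b = 49: (5 × 452 + 55 × 49)/60 = 82.6.

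In a 24-hour mean the one-minute peak adds (452 − 4)/1440 = 0.31 or (452 − 49)/1440 = 0.28 µg/m³. In the planned daily average it is practically invisible.

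**Data volume.** 60 × 24 × 7 = 10,080 records per driver-week.

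**The case against.** The strongest reply is that hourly files are adequate for the analysis as written. With complete data, the mean of hourly means equals the mean of the minute values, so the daily average and AUC would not change. This stands: minute records alone alter no planned PM summary. They pay off only if the in-vehicle summary is also redefined.

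A reader might infer that the minute records are thrown away. The documents do not support that. Section 7.1 says that all data are logged internally, no section gives the logging interval, and the lab manual to which Section 7.1 refers for procedures is not among the documents. What can be said is that the files, the outcome definition and the analysis are all described at hourly resolution, and no use of minute data is planned.

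A reader might also infer that the rationale depends on peaks. It does not. Section 3.0 argues mainly from long-term PM level, particle size and composition, and Aim 1a names no peak measure. A peak summary would be an addition, suitable only as description in a pilot that is descriptive throughout.

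The peak figures have limits too. One minute is the pilot's averaging interval, not necessarily the length of the episode, and the pairing of 452 with backgrounds of 4 or 49 is illustrative. Boundary mixing is modest and could be removed without minute data by dropping two bins per shift, at the price of 8-10% of cab time. Finally, Section 11.0 qualifies its method with "generally" and refers to suitable time periods. That leaves room for a cab-only summary, but none is specified.

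**Conclusion.** The point holds as an inexpensive improvement. There is a real mismatch between one-minute output and the hourly-to-daily-to-28-day chain, applied to a monitor that moves between cab and home while two aims concern in-vehicle PM.

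The larger effect is the whole-day average, in which cab time is 42-50% of a work day. The boundary hours matter less: 15-18% of the bins touched, but only about 8-9% of the time. The loss of brief peaks is clear in direction, with an hourly mean of about 11 to 56 µg/m³ for a one-minute reading of 452, or about 41 to 83 if the peak lasted five minutes.

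These sizes rest on the assumptions listed in the working. If the monitor is off for part of the time at home, the cab share of a daily average would be higher. Nothing here shows that data will be lost or that the planned summaries are computed wrongly.

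**What to change.** 1. Section 7.1, item 1: state the logging interval, and download and retain the one-minute records at each weekly visit.
2. Log-book: add shift start and end times. The items listed in Section 7.1 do not include them, and staff record start and end sampling times only for the black carbon runs.
3. Section 11.0: for Aims 1a and 2, define the in-vehicle PM summary as the mean of the one-minute values between the recorded shift start and end. Report home PM separately, and keep hourly and daily values as secondary. Section 9.1 should be worded to match.
4. If peaks are reported, treat them as descriptive and choose a measure suited to brief events, such as the shift maximum or the minutes above a prespecified level. That level should lie below 400 µg/m³, because the stated range ends there and the pilot maximum of 452 exceeds it; a shift maximum could be capped at 400. A 95th percentile does not suit this purpose: over 600-720 minutes it ignores the highest 30-36 minutes, so a one-minute spike barely moves it.

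The cost is larger files (10,080 records per driver-week), one more log-book item for drivers, a check that the logger can hold a week of minute data, and a little more programming. It is best settled before the first download.
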